- 3. To assess the feasibility of recruiting patients to the study against the criteria of consenting three in every ten eligible patients approached to participate in the study.
- 4. To evaluate the feasibility of the methods of data collection, outcome measurement and economic evaluation in terms of level of missing data and patient acceptability to inform a protocol for a pilot and definitive trial if feasibility and acceptability is apparent.

Research methods

Feasibility study design

The study will use a before and after design to evaluate the process of using the SPACE documents in clinical care and the feasibility of the research methods. Evaluating the feasibility of the research methods will use observation time points:

- 1) Before the incorporation of the SPACE documents in clinical care during the training phase
- 2) After the SPACE documents are used in routine clinical care during the assessment phase.

The design incorporates a process evaluation to explore how the documents are used in clinical practice, the acceptability of the documents and the training and support provided, and identify potential modifiers to improve use and patient benefit ⁴⁵. The study design incorporates the MRC guidance for developing and evaluating complex interventions ⁴⁶ and the MORECare Statement for application in palliative care. ⁴⁷ In keeping with the MRC guidance ⁴⁷, the study uses sequential development and feasibility workstreams to identify, adapt and evaluate the SPACE intervention. This protocol pertains to workstream 4, evaluating the process and acceptability of using SPACE in clinical care and evaluate the feasibility of the research methods to inform a pilot and definitive trial if feasibility and acceptability is demonstrated.

Study setting

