The feasibility study will be undertaken in two community hospitals in Sussex Community NHS Foundation Trust. The trust has 13 community hospitals (inpatient community units) located in West Sussex and East Sussex with approximately 300 inpatient beds. The study is undertaken in West Sussex. This is the locality with the highest proportion of people aged 85 years and over, with the highest corresponding provision of community hospitals. The two hospitals participated in the development workstreams involving consultations with staff and patients. The hospitals will be purposively selected from the four community hospitals involved in the staff consultation workstream three. Purposive selection for the feasibility evaluation is based on the criteria:

- Large facilities to capture a breadth of patients
- Geographical catchment areas of mixed levels of deprivation and ethnicity
- Patients with comparatively high levels of dependency
- Engagement and participation in the preceding development workstream

Study procedures

Selection and withdrawal of patient participants

Eligibility criteria for patients

- An inpatient in the community hospital for 24 hours or more during the study period.
- Aged 65 years or over
- Mental capacity to give informed consent, or for adults lacking capacity availability of an individual who knows them well to complete the research questionnaires

Selection of patient participants

The direct care team will identify potentially eligible patients and approach those meeting eligibility criteria, or for adults lacking capacity approach the nearest caregiver, family member or close friend to act as the personal consultee and/or complete the research questionnaires. The direct care team comprises the clinical teams and/or the clinical research nurses. They will provide patients/consultees with the respective information sheet or post/email to consultees as appropriate. Consultees will receive a follow-up invitation by telephone and/or email. Patients/consultees can decline or indicate interest in participating/advising participation by informing a member of the direct care team. Consultees may also reply via email, telephone or return the reply slip in the Freepost envelope. If no personal consultee is identified, or does not

respond to requests for advice, a nominated consultee will be asked to advise about the person's participation (or not).

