The clinical research nurses/clinical team will maintain a screening log of patients approached as eligible, including consultee approach when required. Table 1 details the clinical information recorded on the screening log. Anonymous data in the screening log is shared with the lead site via NHS email on a monthly basis pending resource and recruitment rate. This is to enable the clinical research nurses and the lead site to review the number of eligible participants screened and approached, and outcome of recruitment or decline and reason when given.

Table 1 Screening log

Clinical information		
1.	Age	
2.	Gender	
3.	3. Admitted from e.g. hospital or home	
4.	Main reason for admission	
5.	Medical diagnoses e.g. frailty, dementia.	
6.	Adult lacking capacity to consent (Y/N). a. Y – personal consultee identified and approached (Y/N) b. No personal consultee, nominated consultee approached	
7.	Reason for declining participation (if applicable, patient or consultee when advice is sought)	

The Mental Capacity Act 2005

We apply the principles of the Mental Capacity Act (MCA) 2005 to include patients who might lack capacity to consent for themselves. The commonality of cognitive impairment in advanced age requires the inclusion of people with impaired mental capacity in the study. Approximately 40% of patients in community hospitals in the study site have dementia or cognitive impairment. Exclusion of people with cognitive impairment would likely exclude those with the highest disease burden, cause bias in the sampling and preclude assessment on the feasibility of recruiting adults lacking capacity.

Advice will be sought from a personal consultee (usually close caregivers/family members) who know the patient sufficiently well to give an opinion as to if the individual would have wanted to participate. If no personal consultee can be identified to advise, a nominated consultee will be approached for advice for example, NIHR Clinical Research Network staff supporting research studies in dementia, the Dementia Lead in the trust, or social worker for community hospitals. Individuals who show distress (verbally or non-verbally) or voice any objection to the study will be withdrawn at any stage and that withdrawal will not affect their usual care.

Raise awareness

The processes of raising awareness is informed by our experiences of consulting staff and patients about the study. We will raise awareness by:

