Feasibility of the research methods

Sample size

The patient total sample size is 40 patients across the two community hospitals, with sample 1 comprising 20 patients and sample 2 comprising 20 patients. We will review the recruitment rate for sample 1, if recruitment is feasible within the timeframe, we will increase the sample 2 size to n=30. The sample size is informed by understanding that feasibility studies should include a minimum of 30 patients, and account for attrition. Attrition is calculated at ~30% as a typical rate for a study in palliative care.⁴⁷ A sample of 40 is considered sufficient for a feasibility study to explore the feasibility of recruitment to the study and the parameters to inform the sample size calculation in a future pilot trial.⁶³ We will recruit a maximum of 12 patients lacking capacity to assess the feasibility of the consultee process to advise on participation, and proxy reporting of research data. Patients lacking capacity will be recruited in sample 1 (pre-SPACE) and sample 2 (after-SPACE embedded). We will review our consultee process in the sample 1 recruitment to identify potential modifiers to enable participation.

Main candidate outcome

We will explore the feasibility and acceptability of a proposed candidate main outcome comprising 'Patient/family anxiety and communication subscale' of the Integrated Palliative Outcome Scale (I-POS)⁶⁴⁻⁶⁶ ⁶⁷ ⁴⁹. Anxiety and communication are common distressing concerns for patients on admission to hospital and their families. These concerns are often exacerbated when clinical presentation is uncertain. The Patient/Family anxiety and communication subscale comprises 7 items of the I-POS⁶⁶. The items concern information, practical matters, shared feelings, at peace, patient anxiety, family anxiety, and patient depression. Items are scored from 0 (best) to 4 (worst) and can be completed by the patient or a proxy (e.g. staff or family member) for adults lacking capacity. The I-POS is the latest refinement and improvement of the well validated and widely used Palliative care Outcome Scale (POS) developed and tested in palliative care⁶⁶. The POS has been used in community and hospital settings, including in nursing homes (UK and the Netherlands), and in many different conditions including dementia,⁶⁷ heart failure⁶⁸, COPD,⁶⁹ cancer, neurological conditions,⁷⁰ and multiple comorbidity⁶⁷.

Secondary candidate outcomes

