- 1. Descriptive analysis on the number of patients screened for eligibility and the proportion of eligible patients recruited and reasons for decline, and differences between participants and non-participants e.g. age, gender
- 2. Descriptive analysis on completion of the SPACE documents from the patient record data extraction on when completed, proportion of missing data, and use over time e.g. IPOS-Dem to review and evaluate outcomes of care.
- 3. Examining the candidate main outcome of *patient/family anxiety and communication subscale* and secondary outcomes. We will examine missing data and evaluate the impact on results. We will explore the before (sample 1) and after (sample 2) measures and degree of change in the candidate main and secondary outcomes using non-parametric test for categorical data (e.g. Chi-Square) or parametric tests for continuous variables (e.g. T-Test).
- 4. Examine reasonable mean and variance estimates of the main outcome to inform the sample size calculation in a future pilot/full trial and estimates of inter-correlation co-efficient by examining variation between hospitals e.g. age, length of stay.
- 5. The data analysis in the economic evaluation will explore procedures to inform the economic evaluation in a pilot/full RCT. Economic evaluation is an emergent area in studies with patients with advanced progressive conditions and uncertainty surrounds best practice ⁷⁶.

Qualitative analysis

We will undertake a full coding of focus group and interview transcripts, non-participant observations and fieldnotes to identify themes using constant comparative approach⁹⁴ in NViVo⁹⁵. Data analysis will explore the range of experiences of staff using the documents in clinical care exploring feasibility and acceptability, solutions and barriers to enhance use, and potential benefit for patients and families. Quality appraisal will use procedures to ensure systematic attention to analysis and reporting e.g. analysis review meetings.

Ethics and regulatory approvals

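### The screening log is defined to cover only approached patients, so it does not secure the screened and eligible denominators that the analysis promises

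*Protocol*

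**What the plan says.** Four parts of the protocol bear on this.

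- **Objectives, objective 3.** Recruitment feasibility is assessed against "consenting three in every ten eligible patients approached to participate in the study". The denominator is eligible patients who were approached. Objective 4 (missing data, acceptability) carries no numerical threshold.
- **Selection of patient participants.** The rule for approach is that "The direct care team will identify potentially eligible patients and approach those meeting eligibility criteria". The clinical research nurses or clinical team "will maintain a screening log of patients approached as eligible, including consultee approach when required". The log is meant to let the nurses and lead site "review the number of eligible participants screened and approached, and outcome of recruitment or decline and reason when given". Table 1 lists seven items of clinical information, including capacity status with consultee approach (item 6) and reason for declining (item 7). It lists no item for eligibility, for approach of patients with capacity, or for the reason a patient was not approached.
- **Quantitative analysis, item 1.** The plan is a "Descriptive analysis on the number of patients screened for eligibility and the proportion of eligible patients recruited", together with reasons for decline and a comparison of participants with non-participants.
- **Sample size.** The target is 40 patients, 20 in each sample, with sample 2 rising to 30 if sample 1 recruits well. Within this, "We will recruit a maximum of 12 patients lacking capacity".

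**The concern.** The log and the analysis have different populations. A log whose rows are approached patients holds nobody who was screened and found ineligible, and nobody who was eligible but not approached. Item 1 needs both groups: the first to count those screened, the second to complete the eligible denominator.

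What is at stake is how the recruitment result can be read when a pilot or definitive trial is considered. A consent rate among those approached says how acceptable the invitation is. It does not say whether those approached represent those eligible. If ward staff pass over some groups, the three-in-ten figure looks the same as if they had not. The protocol itself warns, under The Mental Capacity Act 2005, that leaving out people with cognitive impairment would bias the sample. The log as defined would not detect that if it happened at the approach stage.

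This is not a detail that an analysis plan could supply later. It concerns which rows are collected on the ward, and rows never logged cannot be recovered.

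**Working it through.** **1. What each planned quantity needs, against what the log holds.**

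| Quantity | Source in protocol | Denominator or count needed | Available from the log as defined? |
|---|---|---|---|
| Consented / approached | Objective 3 | Eligible and approached | Yes |
| Number screened | Quantitative analysis, item 1 | All screened | No |
| Recruited / eligible | Quantitative analysis, item 1 | All eligible | Only if every eligible patient is approached |
| Participants v non-participants | Quantitative analysis, item 1 | Non-participants | Those approached who did not take part, only |

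**2. How the two rates relate.**

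recruited/eligible = (consented/approached) × (approached/eligible)

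The 30% criterion is set rather than derived, so there is no figure of the plan's to reproduce. The share approached is not given and cannot be estimated from the documents. With consent among those approached fixed at 30%:

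- all approached: 0.30 × 1.00 = 30%
- three quarters: 0.30 × 0.75 = 22.5%
- half: 0.30 × 0.50 = 15%
- a quarter: 0.30 × 0.25 = 7.5%

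All four meet objective 3, and a log of approached patients cannot tell them apart. These are illustrations over an assumed range, not predictions.

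**3. Does the protocol itself create a route to non-approach?**

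Yes, through the cap. Under The Mental Capacity Act 2005 it states: "Approximately 40% of patients in community hospitals in the study site have dementia or cognitive impairment". Impairment is not the same as lacking capacity, so 40% is at most an indicative upper figure for the share lacking capacity.

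- 40% of 40 recruits = 16, above the cap of 12. With 50 recruits (20 + 30), 40% = 20.
- If consent rates are equal in both groups, the cap binds only when more than 12/40 = 30% of eligible patients lack capacity, or 12/50 = 24% with the larger sample.

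To size the cap alone, assume 40% lack capacity, 30% consent in both groups, 40 recruited, and no approach to patients lacking capacity once 12 are in:

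- recruits with capacity: 40 − 12 = 28, needing 28/0.30 = 93.3 approached
- all eligible: 93.3/0.60 = 155.6, of whom 155.6 × 0.40 = 62.2 lack capacity
- approached lacking capacity: 12/0.30 = 40, leaving about 22 eligible but unapproached
- consented/approached = 40/(93.3 + 40) = 30%
- recruited/eligible = 40/155.6 = 25.7% overall, and 12/62.2 = 19.3% among those lacking capacity

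On these assumptions the cap by itself moves the overall rate modestly, from 30% to about 26%. The shift is larger in the subgroup whose recruitment the study sets out to test.

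**4. Precision, for reporting.** If 40 are recruited, the criterion is met with at most 133 approached (40/0.30 = 133.3). The exact 95% CI for 40/133 = 30.1% is 22.4% to 38.6%. This bears only on how the rate should be presented.

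**The case against.** The strongest reply is that the protocol tells the team to approach those who meet the criteria. If that is done without exception, approached equals eligible and recruited/eligible can be computed. This stands as a statement of intent, and it narrows the point. It does not remove it. The number screened would still be missing, the log could not confirm that the instruction was followed, and the cap gives a reason within the protocol for it not to be.

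Second, Table 1 is headed as clinical information and need not be the whole log. It has no field for recruited or not, although the log is meant to support review of recruitment outcome, so other fields probably exist. Item 6 also partly tracks consultee approach. This is fair, and the absence of fields from Table 1 is weak evidence taken alone. The difficulty lies in the definition of the rows: extra columns do not help if unapproached patients have no row.

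A reader might infer three stronger things, and the documents support none of them.

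- *That the three-in-ten criterion is flawed.* Consent among those approached is a legitimate feasibility measure, and item 1 already intends to report the eligible-based proportion as well.
- *That a trial's accrual would be hidden or halved.* Recruits per hospital are observed directly over the stated windows (2–3 months for sample 1, two months for sample 2), and the Sample size section plans a review of sample 1's recruitment rate. Selective approach cannot inflate the number recruited per month.
- *That most eligible patients would go unapproached.* The protocol gives no eligible count, so the share approached is unknown.

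**Conclusion.** The point holds as a mismatch between the data source and the planned analysis. Followed as written, the log cannot give the number screened. It gives the proportion of eligible patients recruited only if no eligible patient goes unapproached. In that event objective 3 remains computable but cannot show selection at the approach stage.

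The size cannot be fixed from the documents. At 30% consent, recruited/eligible lies anywhere from 30% downwards according to the share approached. The cap alone would bring it to about 26%, assuming that 40% of eligible patients lack capacity, that consent is equal in both groups and that approach stops at the cap. If no more than 30% lack capacity, then with 40 recruits and equal consent the cap does not bind and this route closes. The correction is worth making before recruitment starts, because the missing rows cannot be reconstructed. It does not call the design or the criterion into question.

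**What to change.** In Selection of patient participants, redefine the log as covering every patient screened for eligibility, one anonymous row each. Beside the Table 1 items, record:

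- hospital and sample (1 or 2)
- eligible, yes or no
- approached, yes or no, with the reason if not (including that the cap on patients lacking capacity was reached)
- outcome

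In Quantitative analysis, item 1, keep consented/approached as the criterion for objective 3 and report recruited/eligible beside it. Give each with a 95% confidence interval and split by capacity status.

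The cost is a modest amount of extra logging by staff who already screen. It is not nil: the protocol already makes monthly sharing of the log depend on resource, so the added fields should be kept short. The study timelines show recruitment paused until March 2021, so the log can be changed before the first patient is entered.

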Data collection will take place over two months after embedding the SPACE documents in clinical care in each community hospital. Timepoints will be informed by data completeness in sample 1, and modified if needed, e.g. removing an admission timepoint. Timepoints are planned as:

- 1. 0 to 14 days from the admission date (as soon after the admission as possible)
- 2. 15 to 28 days after admission (or longer if extended admission), and
- 3. After discharge (28-56 days after discharge).

Data collection methods

The methods of data collection will be 'tested' with sample 1 and refined with sample 2 if indicated to enable participation and enhance data reporting quality. The research nurses/researchers will support completion of the research questionnaires with patients during admission. The questionnaire administered on discharge will be posted with a cover letter, reply slip and Free post envelope to return the questionnaire to the research team at King's College London. The research team or the research nurses will assist completion if required by telephone during the COVID-19 pandemic and with face-to face offered after the pandemic (e.g. the person's own home). The research team will follow-up posted questionnaires with two reminders. Reminders will include a telephone call two weeks after postage of the questionnaire (or email, or letter if no phone number is available or calls are unanswered). We will ask the person if we can complete the questionnaire with them over the telephone, or if they prefer to self-complete and return by post. After 4 weeks a reminder letter will be posted with a further questionnaire booklet, reply slip and Free post envelope. The questionnaires will be checked for completeness by the researchers/research nurse, and a follow-up telephone call made to the participant to check accuracy if data is missing or clarify a response when unclear. Prior to posting the final questionnaire, we will check in the community health record if the person has died since discharged.

For adults lacking capacity the questionnaires will be completed by a proxy informant. The proxy informant will be the personal consultee, or another family member (for example the patient's son or daughter) or a close friend. If no family/friend are available the research questionnaire will be completed by a member of the community hospital staff who knows the person, and the post-discharge questionnaire completed by, for example, care home staff. The proxy informant will self-complete the questionnaires on hard-copies either in the hospital or completed at home. Questionnaires will be returned by post to the project team at King's College London. We will make available an online questionnaire if this format is preferred. The proxy informant will be assisted to complete the questionnaires by telephone video call, during the COVID-19 pandemic or face-to-face after the pandemic as required by the research team or research nurses. Only remote interviews will be conducted with consultees during the pandemic. The research team will use two reminders with informants to complete the respective questionnaire. This will include a telephone call two weeks after giving or posting the respective questionnaire (or email or letter will be used if no phone number is available or calls are unanswered). If no response after 4 weeks we will post or email a reminder letter and enclose the respective questionnaire booklet, reply slip and Free post envelope. The questionnaires will be checked for completeness by the researchers/research nurse, and a follow-up telephone call made to the participant to check accuracy if data is missing or to clarify a response when unclear.

Each patient or proxy informant (e.g. the personal consultee or other family member) will receive a thank you card and £5 voucher after completing the data collection during the admission. The card and voucher will be given to the person or posted to their address. The card will thank the person for participating in the study, state that their views are important and that we will ask them to complete a further questionnaire after they (or the person cared for) is discharged. We will post a further thank you card once data collection is completed, thanking the person for participating. The thank you cards will include the research team's contact details and indicate for the person to contact the team if they have any queries or questions about the study.

Distress protocol

There may be some distress and burden in completing the questionnaires and taking part in the study. It is important to note that patients and families often value taking part in research and welcome the opportunity to give their view. We have incorporated the opportunity for open comments, finding that this gives rich supplementary research data and is highly valued by patients and families in being 'heard' by researchers⁵⁹⁻⁶². The research team will have completed Good Clinical Practice training, and specific training on addressing distress. The research nurses and researchers are experienced in recruiting and enabling older people to participate in research studies. We will ensure training and support on approaching patients, assessing capacity and collecting and managing data.

The research nurses and researchers will follow a distress protocol if patients or families become upset during the interviews or are found to be upset or in distress on arrival. Should this be the case they will first offer to pause, postpone or stop the interview and advise again that participation is voluntary. In the case of severe distress, the patient will be encouraged to share his or her feelings with a member of their healthcare team and/or the nurse offers to speak with ward staff with the person's agreement. We anticipate distress caused by the research will be infrequent. Given the general nature of the questions within the measures used, if distress occurs this will likely reflect the individual's concerns about their condition or situation. If participants disclose any ideation of self-harm or other risk to themselves or others, this will be managed as an urgent matter and clinical help will be sought. This will be in agreement with the participant. However, if the researcher/research nurse considers the participant is at imminent risk and refuses to allow voluntary disclosure, the research team will breach confidentiality. Based on prior experience, we anticipate this will be a very rare occurrence. Provision will be made to ensure the researchers have CI or senior back up available by phone whenever they are undertaking data collection. We make it clear that patients and families can omit any questions they don't want to answer and can withdraw at any time from the study with no effect on their usual care. We have ensured that we do not include terms that might be distressing, such as "prognosis", in the information leaflets and questionnaires.

Feasibility of the research methods

Sample size

The patient total sample size is 40 patients across the two community hospitals, with sample 1 comprising 20 patients and sample 2 comprising 20 patients. We will review the recruitment rate for sample 1, if recruitment is feasible within the timeframe, we will increase the sample 2 size to n=30. The sample size is informed by understanding that feasibility studies should include a minimum of 30 patients, and account for attrition. Attrition is calculated at ~30% as a typical rate for a study in palliative care.⁴⁷ A sample of 40 is considered sufficient for a feasibility study to explore the feasibility of recruitment to the study and the parameters to inform the sample size calculation in a future pilot trial.⁶³ We will recruit a maximum of 12 patients lacking capacity to assess the feasibility of the consultee process to advise on participation, and proxy reporting of research data. Patients lacking capacity will be recruited in sample 1 (pre-SPACE) and sample 2 (after-SPACE embedded). We will review our consultee process in the sample 1 recruitment to identify potential modifiers to enable participation.

Main candidate outcome

We will explore the feasibility and acceptability of a proposed candidate main outcome comprising 'Patient/family anxiety and communication subscale' of the Integrated Palliative Outcome Scale (I-POS)⁶⁴⁻⁶⁶ ⁶⁷ ⁴⁹. Anxiety and communication are common distressing concerns for patients on admission to hospital and their families. These concerns are often exacerbated when clinical presentation is uncertain. The Patient/Family anxiety and communication subscale comprises 7 items of the I-POS⁶⁶. The items concern information, practical matters, shared feelings, at peace, patient anxiety, family anxiety, and patient depression. Items are scored from 0 (best) to 4 (worst) and can be completed by the patient or a proxy (e.g. staff or family member) for adults lacking capacity. The I-POS is the latest refinement and improvement of the well validated and widely used Palliative care Outcome Scale (POS) developed and tested in palliative care⁶⁶. The POS has been used in community and hospital settings, including in nursing homes (UK and the Netherlands), and in many different conditions including dementia,⁶⁷ heart failure⁶⁸, COPD,⁶⁹ cancer, neurological conditions,⁷⁰ and multiple comorbidity⁶⁷.

Secondary candidate outcomes

- Palliative concerns not included in the patient/family subscale (I-POS)⁶⁶
- Patient Reported Experience Measure (PREM) from the NHS National Benchmarking of Community hospitals (2018) https://members.nhsbenchmarking.nhs.uk/dashboard/2
 - o I had confidence and trust in the staff treating or supporting me
 - o Overall, I felt I was treated with respect and dignity from this service
- Physical disability (Modified Barthel Index)⁷¹ (during admission timepoints)
- Function (Australian Karnofsky Index for palliative care)⁷² (during admission timepoints)
- Frailty (Fried's Phenotype of Frailty¹) (during admission timepoints). We will review the suitability of Fried's frailty scale for adults lacking capacity in our initially piloting of the questionnaires. The Fried measure includes physical assessment of hand strength, and for people able to walk, a timed 4 meter walk speed. We will review level of missing and feedback from the data collectors. If unsuitable we will remove Fried and replace with *FRAIL* ⁷³. FRAIL score is similar to Fried. FRAIL is very brief (2 minutes) measure of frailty comprising 5 items assessing fatigue, resistance, ambulation, illness and loss of weight. Each item is assessed using a different response option, but no physical measure of sarcopenia
- Survival at 6 months by review of NHS site electronic patient records

Process outcomes

- Community hospital length of stay
- Review and audit of patient records using a data sheet to record completion of the SPACE documents and decision-making³³ e.g. staff involved, completed proxy/selfreport, communication multi-disciplinary teams and with patients and families. Collect completed and de-identified copies of the SPACE documents, including IPOS-Dem, the adapted-PACE and the Anticipatory Care Plan.

Economic evaluation

Comprises EQ-5D⁷⁴ as a quality of life measure recommended in cost-effectiveness analyses and the Client Service Receipt Inventory (CSRI) to record formal inpatient service use, medication and informal care.^{75, 76} The economic data will be recorded in the admission questionnaire reporting the preceding 12 weeks, and repeated in the discharge questionnaire (28-42 days after discharge).

Embedded qualitative study

The embedded qualitative study intends to evaluate the process of using the SPACE documents in clinical practice, the acceptability and feasibility for clinical practice, and identify potential modifiers to enhance use and the potential for benefit, for example, improved communication and holistic assessment. The qualitative study will involve clinical staff in the participating community hospitals. The findings will inform refinements to the documents used in SPACE, solutions and challenges to enhancing and sustaining use in clinical care, potential benefit for patients and families, and methods of evaluation. The embedded qualitative study takes a generic approach that emphasizes common methodological practices across qualitative research methodologies⁷⁷ commonly used in qualitative studies in mixed method feasibility trials.⁷⁸

Data collection

Data collection will involve non-participant observations, focus groups with staff and data from fieldnotes.

Non-participant observations will be of general clinical activity, and specific activities with clinical staff, caregivers and patients. The non-participant observations will be undertaken in both the before and after phases of the study. We estimate 30 observations of clinical practice across the two hospitals. Non-participant observations will include ward rounds and case meetings, staff training, and general activity, and specific observations of for example family meetings (with those present having given informed consent). Observations will be recorded on a A4 sheet with prompts of key areas including: communication (with patients and families, clinical teams); processes of assessment and goals of care; transition in care on discharge; and modifications to enhance document use (e.g. challenges and facilitators). The sheets will detail the date, time, hospital ID number and describe the nature of the observation e.g. case meeting. Observations will be accompanied by informal discussions with staff to clarify issues when indicated.

Focus groups with staff will be undertaken during the before and after phases of the study in each of the community hospitals. We will plan to conduct four focus groups involving 8-10 participants per group. The focus groups will be conducted with staff from the wards to explore the training and procedures for using the SPACE documents (before phase), views on using the SPACE documents and the outcomes (after phase). Additional focus groups will be offered if needed to accommodate staff availability, and individual interviews (or small groups of 2-3 people) to enable all grades and disciplines of staff to participate in the study. The topic guide will explore the processes of using the documents, training and potential to enhance clinical practice and outcomes for patients. The topic areas will include: enhancing key areas of clinical practice (communication with patients/families, comprehensive assessment, and continuity of care on discharge); managing clinical uncertainty; team working and communication; and facilitators and challenges to inform wider use. The topic guide is adapted from our evaluation of the PACE tool.²⁴

Fieldnotes will be taken during staff training in groups or one to one on the use of the SPACE documents in clinical practice, and discussions with them about training and use across the study. The fieldnote data will record a summary of comments and discussions with staff. Fieldnotes will include the date, time, number of people, respective discipline(s) and ID code for the community hospital. No personally identifiable data will be recorded.

Sample size, participants and consent

Non-participant observations will involve caregivers, patients and clinical staff. The caregiver sample will include an estimated 12 caregivers (family member, or close friend) who participate in the non-participation observations of clinical activities, for example, Welcome Meeting on admission, and Family Meeting for discharge planning. The patient sample will comprise individuals recruited to the study with capacity to give informed consent, and patients in the community hospital able to give informed consent to take part in the non-participant observation of for example, the Welcome meeting (total patient observations n=12). The caregiver and patient sample sizes are considered enough to inform understanding on the processes and accessibility of clinical staff using the SPACE documents in clinical practice. The clinical staff will be the staff members involved in the respective clinical activity (e.g. the Welcome meeting, multi-disciplinary team meeting) who give informed consent for the observation. Prior to an observation the researcher (e.g [name], clinical-academic and CI) will reintroduce her/himself, the study and ask if able to observe. If verbally agreed, each person is given an information sheet and the informed consent procedure is completed. At the end of the observation the researcher offers to show the information written down, check again that the person(s) has understood the observation is for a research study, clarify if further questions and offer for the individuals to contact the research team if they have questions about the study.

The focus groups will include 32-40 clinical staff from across the two community hospitals. Staff will be purposively selected to represent the different grades and disciplines of staff delivering care to patients and their families. This will comprise individuals providing care in the wards including those directly employed, and those providing services to the community hospitals, for example, geriatricians, mental health nurses, social worker, caregiver support worker. Staff will be identified by the senior nurses (e.g. ward matron) from each community hospital. They will be approached by the CI/research team by giving them the letter of invitation and information sheet or emailing via NHS email. Two reminder emails will be sent. Informed consent will be completed prior to commencing the focus group (or individual interviews). Some staff may choose to attend on the day of the focus group. They will be given the study information sheet if not received, and the informed consent procedure undertaken.

SPACE intervention

Theoretical underpinning

The SPACE intervention is underpinned by a Theory of Change⁷⁹. This details a conceptual model depicting how the SPACE documents may work in clinical practice, the requirements to support use and linkages with the intended benefits for patients and their caregivers to improve communication and holistic care. The Theory of Change is underpinned by the Uncertainty of Illness theory¹⁶⁻¹⁸ and its application in clinical practice²⁰ in general and specifically for older people²¹, and the earlier stages of the study developing the SPACE intervention for clinical practice.

These earlier stages included:

- Systematic reviews to identify the documents used in SPACE to manage clinical uncertainty for older people with serious illness⁴³, and models of service delivery for older people towards the end of life¹³ (workstream one).
- Stakeholder consultations with staff in four community hospitals exploring the acceptability of using the standardised documents in clinical care, the processes and

- requirements to support use and the potential benefit for patients and families (workstream three)⁴⁴.
- Individual interview administered questionnaires with patients (n=30) in community hospitals on priorities to manage clinical uncertainty focusing on assessment, communication about what to expect, and information transferred on discharge (workstream three)⁴⁴.
